16.4.4.1 Objective Response: Logistic Regression Model

Multivariate logistic regression of the following form will be used to evaluate potential relationships between OR and exposure:

$$\text{logit}(P) = \log\left(\frac{P}{1-P}\right) = \beta_0 + \beta_1 \cdot C + \beta_2 \cdot X_2 + \beta_3 \cdot X_3 + \dots + \beta_n \cdot X_n \quad (1)$$

Where P represents probability of being responder, β_0 hypothetically represents the odds of the event occurring without any exposure. β_1 represents a linear effect of the exposure. C represents exposure metric. β_j represents the estimate of the effect of an additional covariate where $j = 2, \dots, n$ and for a total of $n-1$ covariates (X_n).

16.4.4.2 Objective Response: Nonlinear logistic regression

The classical logistic model assumes linear relationship of the logit with exposure, meaning that probability of response can asymptotically reach 100% for an infinite exposure, which is unrealistic. Therefore, an exploratory nonlinear logistic regression will be performed using an Emax function (Equation 2) instead of the linear function as shown in Equation 1.

$$\text{logit}(P) = \log\left(\frac{P}{1-P}\right) = \beta_0 + \frac{Emax \times C}{C+EC50} \quad (2)$$

Here, P is the probability of response, β_0 hypothetically represents the odds of the event occurring without any exposure, Emax is the maximum drug effect, EC50 is the exposure level where 50% of maximum drug effect is reached. C represents exposure metric

16.4.4.3 Overall survival and progression free survival: Cox Proportional Hazards Model

Progression free survival (PFS) and overall survival (OS) were captured as events and non-events and therefore the drug exposure response model will be developed using time-to-event analysis. A Cox proportional hazards model will be used to assess the relationship for OS and PFS versus avelumab exposure as well as to explore prognostic factors (covariates) for each endpoint. The exposure metrics will include, but are not limited to, $C_{\text{trough_sd}}$, $C_{\text{trough_ss}}$ and AUC_{ss} , AUC_{sd} . Validity of the assumption of proportionality of hazards for the covariates could be verified by residual analysis (plots). Maximum likelihood estimates of the parameters will include hazard ratios and 95% confidence intervals.

The Cox proportional hazards model is the most commonly used multivariate approach for analyzing survival time data in medical research. It is a survival analysis regression model, which describes the relation between the event incidence, as expressed by the hazard function and a set of covariates. Mathematically, the Cox model is written as:

$$h(t) = h_0(t) * \exp(\beta_1 \cdot C + \beta_2 \cdot X_2 + \beta_3 \cdot X_3 + \dots + \beta_n \cdot X_n) \quad (3)$$

Where the hazard function $h(t)$ is dependent on (or determined by) a set of n covariates (C, x_2, \dots, x_n) including exposure metric (C), whose impact is measured by the size of the respective

regression coefficients $(\beta_1, \dots, \beta_n)$. An appealing feature of the Cox model is that the baseline hazard function $h_0(t)$ is estimated non-parametrically, and so unlike most other statistical models, the survival times are not assumed to follow a particular statistical distribution.

The Cox model is essentially a multiple linear regression of the logarithm of the hazard on the covariables, with the baseline hazard being an ‘intercept’ term that varies with time. The covariates then act multiplicatively on the hazard at any point in time, and this provides us with the key assumption of the proportional hazards model: the hazard of the event in any group is a constant multiple of the hazard in any other. In case of ties, the discrete logistic likelihood

$$L(\beta_1, \dots, \beta_n) = \prod_{i=1}^k \frac{\exp(\beta_1 \sum_{j \in D_i} C_j + \dots + \beta_n \sum_{j \in D_i} X_{nj})}{\sum_{q \in Q_i} \exp(\beta_1 \sum_{l=1}^{d_i} C_{q_l} + \dots + \beta_n \sum_{j \in D_i} X_{nq_l})} \quad (4)$$

is maximized for the estimation of regression coefficients. The term D_i in equation (4) denotes the set of subjects failing at time point i for distinct event time points $i = 1, \dots, k$ (with d_i as number of subjects failing at time point i). The set Q_i includes all d_i -tuples (q_1, \dots, q_{d_i}) of subjects, which are under risk at time point i .

Correlation plots will be produced to explore co-linearity of relevant covariates to exposure and correlation coefficients will be reported.

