7.1.2.2 Expansion Phase

During the treatment period, the following assessments will be performed (see Appendix I for the detailed schedule):

- AEs and concomitant medications will be documented in each study visit.
- ECOG performance status will be assessed prior to trial treatment at Day 1 (unless the screening ECOG was performed within 3 days prior to Day 1) and every 2 weeks thereafter.
- Physical examinations will be performed prior to trial treatment in each visit until Week 13 (except Day 2 and Day 3), and every 6 weeks thereafter.
- Vital signs and body weight will be assessed prior to trial treatment in each visit until Week 13 (except Day 2 and Day 3), and every 2 weeks thereafter.
- The 12-lead ECGs (assessed prior to infusion and 2 hours \pm 20 minutes after infusion) will be assessed every 2 weeks until Visit 13, and every 6 weeks thereafter.
- The laboratory hematology and hemostaseology tests will be assessed prior to trial treatment and every 2 weeks thereafter.

- Full serum chemistry will be assessed prior to trial treatment, at Week 7 and Week 13 and then every 6 weeks thereafter. Core serum chemistry will be performed at Week 3, Week 5, Week 9 and Week 11 and every 2 weeks thereafter; if a full and core chemistry are scheduled at the same visit only the full chemistry will be performed. In addition, for subjects with liver metastases at baseline, samples for ALT, AST, total bilirubin, and alkaline phosphatase determination will be collected at Weeks 2, 4, and 6. Full urinalysis will be performed at screening and a basic urinalysis will be performed prior to trial treatment as defined in [Appendix I](#) (except for subjects with urothelial cancers, whose urine is usually unfit for analytical purposes).
- The urine β -HCG pregnancy test will be performed every 4 weeks in premenopausal women (before administration of the study drug).
- The tumor evaluation (see Section 7.3) will be performed at Week 7, and then once every 6 weeks for the first 12 months then every 12 weeks thereafter, with a tumor assessment visiting time window of 5 days prior to dosing.

Melanoma and mesothelioma: For subjects in the melanoma and mesothelioma cohorts only, fresh biopsies may be obtained on Day 43. These biopsies are optional.

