16.2 Secondary Endpoint Analyses

Clinical efficacy parameters will be analyzed descriptively in the FAS, and, in addition, for the urothelial carcinoma efficacy expansion cohort, in the PD-L1 positive FAS. Pooling of data from subjects with at least 6 months follow-up period in the urothelial carcinoma efficacy and secondary cohorts may be considered to enhance precision of estimates if data is sufficiently homogeneous. The following efficacy endpoints will be considered: The confirmed and unconfirmed BOR, per RECIST 1.1, as adjudicated by an IERC and per investigator assessment; irBOR according to modified irRC per investigator assessment, DR, TTR, and PFS time according to RECIST 1.1 criteria per IERC and investigator assessment; DR, TTR, and irPFS time according to irRC criteria

per investigator assessment; OS time. Subgroup analyses specified in Section 16.2.6 and summary of demographics will also be presented for pooled population.

The percent change in target lesions from baseline will be derived as:

- $((\text{Sum of target lesions at week XX} - \text{sum of target lesions at baseline}) / \text{sum of target lesions at baseline}) * 100\%$

The maximum reduction in target lesions from baseline will be derived across all the post-baseline assessments as:

- Minimum of $((\text{sum of target lesions at week XX} - \text{sum of target lesions at baseline}) / \text{sum of target lesions at baseline}) * 100\%$

The tumor shrinkage will be calculated based on investigator assessment for all the expansion cohorts and, in addition, based on IERC data for efficacy expansion cohorts and the urothelial carcinoma secondary cohort. The percent change from baseline in target lesions per time point as well as other relevant information will be presented in a data listing. The percent change from baseline in target lesions as well as the first occurrence of new lesion and subject off treatment overall and by PD-L1 expression status will be displayed against time point (weeks) in spider plots. The maximum reduction from baseline in the sum of target lesion diameters overall and by PD-L1 expression status will be presented per subject in waterfall plots. The PD-L1 expression status will be displayed using different colors or line styles in the plots. The time point of a tumor assessment per investigator is defined as the earliest scan date of the respective visit.

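### The exposure-response Cox models in expansion SAP 16.4.4.3 promise hazard ratios but handle ties with a likelihood that estimates odds ratios; for PFS the likely excess is about 1–4% on the log scale

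*SAP*

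**What the plan says.** These statements are in expansion SAP 16.4.4.3 unless another place is named.

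- **Model.** "A Cox proportional hazards model will be used to assess the relationship for OS and PFS versus avelumab exposure". Equation (3) is the usual proportional hazards form, so each coefficient is a log hazard ratio. The key assumption is given as: "the hazard of the event in any group is a constant multiple of the hazard in any other".
- **Output.** "Maximum likelihood estimates of the parameters will include hazard ratios and 95% confidence intervals".
- **Ties.** "In case of ties, the discrete logistic likelihood", printed as equation (4), "is maximized for the estimation of regression coefficients". The section does not say that the exponentiated coefficients then change meaning.
- **Status.** SAP 16.4.4 calls this exposure-response work exploratory and confines it to the secondary and efficacy urothelial cohorts.
- **When PFS events are seen.** In Protocol 7.1.2.2 the tumour evaluation "will be performed at Week 7, and then once every 6 weeks for the first 12 months", "with a tumor assessment visiting time window of 5 days prior to dosing". SAP 16.2 uses actual scan dates: "The time point of a tumor assessment per investigator is defined as the earliest scan date of the respective visit".

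**The concern.** Equation (4) compares the subjects who fail at a given time with every set of the same size that could have been drawn from those at risk. That is the conditional logistic likelihood, which suits time that is truly discrete. Its coefficient is a log odds ratio for failing at that time. With a single event at a time it reduces to the ordinary Cox partial likelihood, so the mismatch arises only at ties.

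Progression happens in continuous time but is seen at 6-weekly scans, so PFS events bunch and ties will occur. The reported hazard ratio for exposure would then be an odds ratio, and the discrepancy always runs away from 1. Estimates of this kind are used in the programme: Protocol 3.5.1 cites preliminary exposure-efficacy relationships, including Cox models in NSCLC, in support of the once-weekly cohort.

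**Working it through.** The section states no hazard ratio, power or sample size, so there is no planned figure to reproduce.

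**1. Is equation (4) the conditional logistic likelihood?** It was coded with the last denominator sum running over l = 1 to d_i, like the first. On a simulated test data set it gave a coefficient of −0.4574. Conditional logistic regression stratified on risk sets also gave −0.4574. The two are the same likelihood.

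**2. Inputs.**

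- Scan interval of 42 days and a 5-day window, giving six possible calendar days per visit (Protocol 7.1.2.2).
- Subjects: at least 109 from the efficacy cohort (SAP 16.4.4) plus 44 from the secondary cohort (Protocol 3.5.5.3), so 153. The upper bound is 44 + 200 = 244.
- Median PFS: assumed to be 1.5 to 6 months. The only anchor is the figure of about 3 months for second-line agents in Protocol 3.5.3.
- True hazard ratios of 0.50 (binary covariate) and 0.70 (per SD): assumed.

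**3. Closed form under proportional hazards.** Let w be the grouping width in days and m the median PFS in days (months × 30.4375). Then:

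- p0 = 1 − 2^(−w/m)
- p1 = 1 − (1 − p0)^HR
- OR = p1(1 − p0) / [p0(1 − p1)]

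Example with HR 0.50, median 3 months (m = 91.3) and w = 42: p0 = 0.2730 and p1 = 1 − √0.7270 = 0.1474. OR = (0.1474 × 0.7270)/(0.2730 × 0.8526) = 0.460. The log-effect ratio is ln 0.460 / ln 0.50 = 1.12.

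Each cell gives the odds ratio and the inflation of the log-effect:

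| True HR | Grouping | Median 1.5 months | 3 months | 6 months |
|---|---|---|---|---|
| 0.50 | 42 days | 0.421 (25%) | 0.460 (12%) | 0.480 (6%) |
| 0.50 | 6 days | 0.489 (3%) | 0.494 (2%) | 0.497 (1%) |
| 0.70 | 42 days | 0.631 (29%) | 0.666 (14%) | 0.683 (7%) |
| 0.70 | 6 days | 0.690 (4%) | 0.695 (2%) | 0.698 (1%) |

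The 42-day rows describe every scan of a visit falling on one study day. The 6-day rows are a rough guide to scans spread over the window, where six possible days per 42-day cycle carry about 42/6 = 7 days of risk each. With 1-day grouping, as for exact death dates, the inflation is at most 0.6% over these medians. At HR = 1, p1 = p0 and OR = 1, so the null value does not move.

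**4. Simulation.** There were 80 replicates per scenario, exponential PFS, 6-weekly scans, 6 to 12 months of follow-up and deaths as 0 or 15% of events. All of these are assumptions.

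- **No ties:** the discrete and Efron estimates are identical.
- **Scans spread over the 5-day window (15% deaths):** the largest tie averaged about 8 to 18 events. For true 0.50 the discrete estimate was 0.478 to 0.498 and Efron 0.484 to 0.508. For true 0.70 they were 0.695 to 0.697 and 0.701 to 0.706. The discrete log-effect exceeded Efron's by 1.5 to 4%.
- **All scans on the nominal day:** at a 3-month median, true 0.50 gave 0.44 to 0.47 with the discrete method and 0.49 to 0.50 with Efron. At 1.5 months the discrete method gave 0.41 to 0.45. Across all such settings the discrete log-effect exceeded Efron's by 9 to 43%.

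The Monte Carlo standard error of the mean log estimate was about 0.02 for the binary covariate and 0.01 for the continuous one. The paired discrete-to-Efron comparison is therefore more informative than either method's distance from the true value.

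**The case against.** The strongest reply is that the consequence is negligible. Much in the plan breaks up ties:

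- actual scan dates and the 5-day window;
- extra scans at the investigator's discretion (Protocol 7.3);
- deaths within 84 days counted on their own dates (SAP 16.2.3);
- dose delays, anticipated in SAP section 15, which shift scans tied to dosing.

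The covariates are chosen stepwise at 15% and 40% thresholds, with final inclusion left to judgement (SAP 16.4.4), so a shift of a few per cent would not change an interpretation. The SAP also prints the likelihood it maximises and hides nothing.

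All of that stands as a limit on size. It does not remove the mismatch: the section specifies one model, estimates the parameter of another, and labels the result with the first.

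A reader might infer more than the documents support:

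- **A double-digit exaggeration.** This needs nearly all scans on one study day, which the dating rules do not imply.
- **That every reported estimate lies beyond the true hazard ratio.** The statement concerns what is being estimated. With scans spread over the window, the simulated discrete means were within about one Monte Carlo standard error of the true value in nearly all settings and under two in all.
- **That all Cox models in the SAP are affected.** The PD-L1 subgroup models in SAP 16.2.6 state no tie method.
- **That OS is distorted.** Death dates produce few ties.

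**Conclusion.** The point holds as an estimand mismatch confined to the exploratory urothelial exposure-response models of SAP 16.4.4.3, and in practice to PFS. Hazard ratios are promised, and conditional odds ratios are estimated wherever events tie. Under proportional hazards the odds ratio is the further from 1.

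The likely excess on the log scale is about 1–4%, assuming that PFS in these models is dated by actual scans spread over the window. SAP 16.2 says this explicitly for investigator assessments. If most scans shared a study day, a true 0.50 would appear as 0.46 at a 3-month median PFS and 0.42 at 1.5 months; both medians are assumptions. No confirmatory test, alpha or sample size is involved. This is a minor correction, worth making because it is cheap and the discrepancy has a fixed direction.

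**What to change.** In SAP 16.4.4.3, replace equation (4) and the definitions that follow it with Efron's approximation, or with the exact (marginal) likelihood for continuous time, so that the reported hazard ratios belong to equation (3). If equation (4) is kept, label the estimates as discrete-time odds ratios.

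In SAS or R, the software named for these models, the change is a tie option. It needs a short rewrite of the equation and its notation rather than a single sentence. The data cut-off for this analysis was 19 March 2016 and SAP version 9.0 is dated 10 February 2017, so the change comes after the cut-off and should be documented as such. Efron's method does not address the interval censoring caused by 6-weekly scans, which is a separate limitation.

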16.5 Immunogenicity

ADA (referred to as HAHA in CRF and SDTM) was assessed before the study treatment start, and on Days 15, 29, 43, 57, 71, 85, 127, and 169 prior to the start of infusion, and at the end of treatment visit. If the sample is positive for ADA, it will be re-analyzed to determine the titer and nAb. The ADA results will be derived based on the algorithm in Table 9. Subjects will be characterized into different ADA categories based on the criteria in Table 10.

Table 9 Algorithm for the Derivation of ADA Results

Sample Screen Result	Confirmatory	Titer	ADA Result
Negative	NA	NA	Negative
NR	NA	NA	NR
Positive	Negative	NA	Negative
Positive	NR	NA	NR
Positive	Positive	Number	Number
Positive	Positive	NR	Positive-TNR

NR = no result, NA = not applicable, TNR = titer no result.

Table 10 Subjects Characterized based on ADA Results

Category	Definition	Subject at Risk (Denominator for Incidence)
Never positive	No positive results at any time point	Number of subjects with at least one valid result at any time point
Ever positive	At least one positive result at any time point	Number of subjects with at least one valid result at any timepoint
Pre-existing	A positive ADA result prior to treatment with avelumab	Number of subjects with valid baseline result
Treatment boosted	A positive ADA result prior to treatment with avelumab and the titer ≥ 8 *baseline titer while on avelumab treatment	Number of subjects with valid baseline and at least one valid post-baseline result
Treatment emergent	Not positive prior to treatment with avelumab and with at least one positive post-baseline result	Number of subjects with at least one valid post-baseline result and without positive baseline results (including missing, NR)
Transient positive	If treatment emergent subjects have (a single positive evaluation, or duration between first and last positive result <16 weeks) and last assessment not positive.	Number of subjects with at least one valid post-baseline result and without positive baseline results (including missing, NR)
Persistent positive	If treatment emergent subjects have duration between first and last positive result ≥ 16 weeks or a positive evaluation at the last assessment	Number of subjects with at least one valid post-baseline result and without positive baseline results (including missing, NR)

Samples with a reportable ADA titer will also be tested in the neutralizing antibody (nAb) assay. NAb results are positive or negative in a single assay and only derived when not performed because ADA was negative (see Table 11). Subjects will be characterized into different nAb categories based on the criteria in Table 12. For nAb, treatment-boostered is not applicable since no titer result is available.

Table 1 Algorithm for the Derivation of nAb Results

ADA Confirmatory Result	nAb Result	Derived nAb Result
Negative	NA	Negative
NR	NA	NR
NA	NA	Negative
Positive	NR	NR
Positive	Positive	Positive
Positive	Negative	Negative

ADA = antidrug antibody, NA = not applicable, nAb = neutralizing antibody, NR = no result.

Table 2 Subjects Characterized based on nAb Results

Category	Definition	Subject at Risk (Denominator for Incidence)
Never positive	No nAb positive results at any time point	Number of subjects with at least one valid ADA result at any time point
Ever positive	At least one nAb positive result at any time point	Number of subjects with at least one valid ADA result at any time point
Pre-existing	A positive nAb result prior to treatment with avelumab	Number of subjects with valid ADA baseline result
Treatment emergent	Not nAb positive prior to treatment with avelumab and with at least one nAb positive post-baseline result	Number of subjects with at least one ADA valid post-baseline result and without nAb positive baseline results (including missing, NR)
Transient positive	If treatment emergent subjects have (a single nAb positive evaluation, or duration between first and last nAb positive result <16 weeks) and last ADA assessment not nAb positive.	Number of subjects with at least one ADA valid post-baseline result and without nAb positive baseline results (including missing, NR)
Persistent positive	If treatment emergent subjects have duration between first and last nAb positive result ≥16 weeks or a nAb positive evaluation at the last ADA assessment	Number of subjects with at least one ADA valid post-baseline result and without nAb positive baseline results (including missing, NR)

ADA = antidrug antibody, nAb = neutralizing antibody, NR = no result.

The frequency and percentage of each ADA and nAb category will be presented in tables by cohort. Listings of ADA and nAb results from ADA ever-positive subjects will be prepared.

For the ADA ever-positive subjects, a listing will be prepared by cohort with subject ID, start and stop of treatment, date of onset, time to onset (weeks since treatment start) and last date of ADA positive results, as well as date of onset, time to onset and last date of nAb positive results, confirmed BOR and confirmed BOR date, DOR, PFS time or censoring time and reason for censoring, and OS time or censoring time and reason for censoring. Confirmed BOR will be based upon IERC results for the efficacy expansion cohorts and secondary UC cohort and investigator results otherwise.

For the ADA ever-positive subjects by cohort, the percent change from baseline in target lesions as well as the first occurrence of a new lesion and subject off treatment will be displayed against time point (weeks) in a line plot. Additional symbols will indicate the first and last ADA positive result and, if applicable, the first and last nAb positive result.

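### Expansion SAP 16.5 counts ADA-positive subjects who have no nAb result as nAb never positive, which understates nAb incidence if there are any such subjects

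*SAP*

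**What the plan says.** All of this is in Section 16.5 of the expansion SAP. The nAb derivation and nAb category tables are printed there as Table 1 and Table 2, but the text calls them Tables 11 and 12; the text's numbers are used here.

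- **Which samples are tested.** The opening paragraph says: "If the sample is positive for ADA, it will be re-analyzed to determine the titer and nAb". The paragraph before Table 11 is narrower: "Samples with a reportable ADA titer will also be tested in the neutralizing antibody (nAb) assay". Table 9 provides for a confirmed positive without a titre: "Positive Positive NR Positive-TNR".
- **When an nAb result is derived.** The text says that nAb results are "only derived when not performed because ADA was negative". Table 11 is keyed on the ADA confirmatory result. Its row for confirmatory not applicable reads "NA NA Negative". Its row for an ADA-positive sample without an nAb result reads "Positive NR NR".
- **How subjects are classified.** In Table 12, never positive requires only that no sample is nAb positive. The denominator for ever and never positive is "Number of subjects with at least one valid ADA result at any time point". The other Table 12 denominators also rest on a valid ADA result.

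**The concern.** Table 11 keeps a missing nAb result apart from a negative one, and Table 12 then discards that distinction. Under the derivation rules a positive nAb result can come only from an ADA-positive sample. ADA-positive subjects without a result are thus the ones whose status is truly unknown, and the plan reports them on the reassuring side. The ADA categories in Table 10 do not have this feature, because their denominators require a valid result from the assay being reported.

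The expansion SAP (Section 16) lists neutralizing capacity among its secondary endpoints, and frequencies are tabulated by cohort. Two secondary cohorts, CRC and CRPC, plan 20 subjects each, where one misclassified subject moves the percentage by 1/20 = 5 points.

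**Working it through.** The documents state no ADA or nAb incidence, so there is no figure to reproduce. The check follows samples through the tables and then illustrates the size.

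**1. Sample level**

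| Sample | ADA result (Table 9) | nAb result (Table 11) |
|---|---|---|
| Screen negative | Negative | Negative |
| Screen no result | NR | Negative |
| Confirmatory negative | Negative | Negative |
| Confirmatory no result | NR | NR |
| Positive with titre, nAb done | Positive | As measured |
| Positive with titre, nAb no result | Positive | NR |
| Positive, no titre, nAb not run | Positive-TNR | No explicit row |

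**2. Subject level.** A subject whose only ADA-positive sample is of either of the last two kinds has a valid ADA result and so enters the denominator. No sample is nAb positive, so the class is never positive. If that sample is the baseline one, the subject is likewise in the pre-existing denominator and not in its numerator.

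**3. Effect of the confirmatory-NA row.** Table 9 gives confirmatory NA in two cases: screen negative ("Negative NA NA Negative") and screen no result, where the ADA result is NR. Only the second is mislabelled. Taking every history of four samples over eight sample states (8^4 = 4096; the seven above, with nAb done split into positive and negative) and recoding screen-no-result samples from Negative to NR changes ever positive, never positive, pre-existing, treatment emergent and their denominators in 0 histories. The reason is structural: each denominator needs a valid ADA result, and no incidence category separates Negative from NR.

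**4. Size.** N = 1640 is the expansion total in protocol Section 8.1. The rest are assumptions: 5% ADA positive, so P = 82; nAb-positive share among those tested r = 0.60; U = ADA-positive subjects without any nAb result.

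- As planned: (P − U)r / N
- U removed from the denominator: (P − U)r / (N − U)
- U given the same rate: Pr / N
- Upper bound, all U positive: ((P − U)r + U) / N

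| U / P | U | As planned | U removed | Same rate | Upper bound |
|---|---|---|---|---|---|
| 0% | 0 | 3.00% | 3.00% | 3.00% | 3.00% |
| 10% | 8.2 | 44.28/1640 = 2.70% | 44.28/1631.8 = 2.71% | 49.2/1640 = 3.00% | 52.48/1640 = 3.20% |
| 25% | 20.5 | 36.9/1640 = 2.25% | 36.9/1619.5 = 2.28% | 49.2/1640 = 3.00% | 57.4/1640 = 3.50% |

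The planned figure is (1 − U/P) times the same-rate figure, so the relative understatement is U/P for any N. Over assumed ranges of 3–10% ADA positive, U/P of 5–50% and r of 30–90%, the relative understatement is 5–50%. The absolute gap runs from 0.03 × 0.05 × 0.30 = about 0.05 points to 0.10 × 0.50 × 0.90 = 4.5 points. Removing U from the denominator recovers at most about 0.24 points (4.50% to 4.74%), because the loss is in the numerator.

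**The case against.** The best reply is that the effect is conditional and may be nil: no rate of missing nAb results or missing titres is given, and with none missing the tables are right. That stands, and it is why the point is worded conditionally.

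The existing row for an ADA-positive sample with no nAb result can be read to cover an untested one, since NR means no result. That is fair at sample level, but the subject-level class is the same either way. Protocol Sections 7.7.1 and 8.5.3.3 provide for characterising ADA-positive samples for neutralizing antibodies. That supports the SAP's wider testing sentence but does not remove its narrower one, and expansion SAP Section 9 does not list the restriction as a change.

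The planned listings for ADA ever-positive subjects would let a reader find the missing results. They do not correct the tabulated percentages. It is also true that these analyses are exploratory (protocol Section 8.5.1) and that no decision rule uses nAb.

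A reader might infer two further things that the documents do not support:

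- *That the confirmatory-NA row itself lowers incidence.* It mislabels screen-no-result samples, against the text, but step 3 shows that no incidence category moves.
- *That this row turns persistent subjects into transient ones.* Transient requires only that the last assessment is not nAb positive, and NR is not positive either. The split moves (105 of the 4096 histories) only if last is read as last valid, which the SAP does not say.

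**Conclusion.** The point holds in conditional form. As written, Table 12 classes an ADA-positive subject without an nAb result as never positive and keeps that subject in the denominator. Ever-positive and pre-existing incidence is then understated if any such subject exists. The relative size equals the missing share only if these subjects have the nAb rate of tested ADA-positive subjects; the rates used above are assumptions. It would go too far to say that incidence is understated outright.

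The direction is not fixed for treatment-emergent nAb. An untested ADA-positive baseline counts as not nAb positive, so a later positive can be called emergent, which pushes that figure up.

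The two testing sentences conflict, and the confirmatory-NA row conflicts with its text. The first can add to the missing share; the second is a labelling error with no effect on incidence. This is a minor but definite correction.

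**What to change.** 1. Key the nAb derivation on the final ADA result in Table 9: Negative gives Negative, NR gives NR, and any positive without an nAb result, Positive-TNR included, gives NR.
2. Reconcile the two testing sentences so that Positive-TNR samples are tested, as the opening paragraph of Section 16.5 says.
3. Give subjects with at least one ADA-positive sample lacking an nAb result, and no nAb-positive sample, their own category (ADA positive, nAb not evaluable) instead of never positive. Report its count by cohort, and show nAb incidence both with these subjects excluded and as an upper bound counting them as positive.
4. State that transient and persistent use the last valid assessment.

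Merely requiring a valid derived nAb result in the denominator would not be enough. A subject who is ADA negative at baseline, ADA positive with nAb NR on Day 15 and ADA negative on Day 29 has two derived negatives, so would stay in the denominator as never positive.

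The cost is edits to the tables and minor programming, plus the nAb runs on Positive-TNR samples. Reported nAb incidence may come out slightly higher.
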